Multimodal Analysis and
Electroretinogram in VKH
From Acute Onset - Part I

NCT03811366

03/26/2025

STUDY PROTOCOL

Prospective cohort study on VKH disease conducted from June 2011 through January 2017 at Uveitis Service, Hospital das Clinicas HCFMUSP, Faculdade de Medicina, Universidade de Sao Paulo, SP, BR. The local institutional review board approved the full protocol, which follows the tenets of the declaration of Helsinki (clinicaltrials NCT03811366).

The inclusion criteria consisted of: diagnosis of VKH disease in the acute phase according to the International Committee in 2001 [1]. The exclusion criteria were: less than a 24-month follow-up period and contraindication to corticosteroid therapy. Treatment protocol included a three-day course of intravenous methylprednisolone (1000 mg per day) followed by a high dose of oral prednisone (1.0 mg/kg/day) with a slow tapering with dose equal or less than 0.1mg/kg/day after 10 months. The prednisone dose was scheduled to be reduced in a 0.1 mg/kg-step ladder until it reaches 0.3 mg/kg (i.e., for an individual with 60 kg, dose would be 20 mg): from 1 to 0.8 mg/kg every two to three weeks; at 0.7 mg/kg for 4 weeks; at 0.6 mg/kg for two to three weeks; from 0.5 mg/kg every 4 weeks; from 0.3 to 0.15 mg/kg every 6 weeks; and 0.1 mg/kg, 0.075 mg/kg and 0.05 mg/kg for 8 weeks each. Oral corticosteroid dose increase was prescribed in case of persistent clinical inflammation signs in two steps and at least 0.5 mg/kg/d. For example, if a patient with 60 kg presents worsening of inflammatory signs while in use of 0.4 mg/kg/d, oral corticosteroid should be increased to 0.6 mg/kg/d. On the other hand, if a patient with 60 kg presented a clinical flare while using 0.2 mg/kg/d, the oral corticosteroid should be increased to at least 0.5 mg/kg/d. Subsequent tapering would be performed as previously scheduled. Additional non-steroidal immunosuppressive therapy (IMT) would be prescribed if the patient presented intolerance due to side effects (e.g., psychosis) or prednisone monotherapy-refractory inflammation. IMT use would be considered as an additional therapy if implemented for at least six months and if includes cyclosporine A, azathioprine, or mycophenolate mofetil.

Examinations were performed at inclusion, 1, 2, 4, 6 months (M), and, thereafter, every 3 months. Each visit included complete clinical and imaging examinations (e.g., fundus color photography, ICGA, fluorescein angiography – FA and EDI-OCT). ff-ERG was performed at inclusion; at 30 days and at 6 months intervals thereafter, using RETI-port system (Roland Consult; Electrophysiological Diagnostic Systems, Brandenburg, Germany). Fundus color photography was performed using the Topcon

TRC-50DX (Tokyo, Japan); FA, ICGA and EDI-OCT were performed using Spectralis® HRA+OCT (Heidelberg Engineering, Germany). Fundus findings were graded according to a previously described analytical framework [2]. The development of sunset glow fundus was classified as either present or absent based on the fundus color photography. Imaging examinations were read by two well-trained examiners. In case of instances of disagreement, the senior reader would classify the images and would be responsible for the final decision. The FA and ICGA reading charts were adapted from Tugal-Tutkun et al [3]. Dark dots (DD) were evaluated based on a semi-quantitative score for the posterior pole and each quadrant: sparse and/or faint and numerous and/or pronounced. The total score varies from 0 to 8. Fluctuation was defined as a change in DD quantity (e.g., sparse to numerous or vice versa) according to the Tugal-Tutkun et al score and whether the DD in the posterior pole or in each quadrant [3]. Objectively, DD fluctuation was defined as a final score variation ≥ 0.5 between two different points in time. ff-ERG recordings were performed in accordance with the International Society for Clinical Electrophysiology of Vision guidelines with the RETI-port system (Roland Consult) using ERG-jet electrodes (Universe SA, La Chaux-deFons, Switzerland) [4]. Scotopic ERG responses were recorded after a period of 20 minutes of dark adaptation, and photopic ERG responses were recorded after 10 minutes of light adaptation. The recording sequence was scotopic rod response, scotopic cone–rod combined response, scotopic oscillatory potentials, photopic cone response, and 30-Hz flicker cone response. The normal value limits for each specific ERG response were established at 95% confidence intervals. Amplitude and implicit time of a and b wave of eight averaged stimulus response for each phase were analyzed, and the results were compared with a normative database. The worsening of the ERG parameters was defined as value reduction $> 30\%$ in any scotopic ERG parameter, which needed to be confirmed in two consecutive examinations [5]. ff-ERG scotopic parameters obtained at 12 and 24 months were compared; all included eyes were grouped based on the worsening or stabilization of the scotopic parameters from 12th to 24th month.

After the acute inflammatory phase (six months following disease onset), disease activity was systematically evaluated based on both clinical and subclinical signs. Specifically, clinical signs included anterior chamber cells (ACC) of at least 1+ cells, exudative retinal detachment, and macular edema confirmed on FA and/or OCT. Visual acuity measurement with a Snellen chart was converted to LogMAR values. Subclinical

signs are those detected exclusively in posterior segment imaging (PSI) and included optic disc leakage/hyperfluorescence (ODH) and/or perivasculär leakage on FA; hypofluorescent DD on ICGA; and, increase of at least 30% in subfoveal choroidal thickness (CT) in two consecutive EDI-OCT examinations. Perivasculär leakage was observed as an increase in hyperfluorescence around retinal vasculature over time on FA exam at midperiphery. Isolated subclinical signs of activity did not infer change in treatment schedule, whereas clinical signs led to either an increase in a daily oral prednisone dosage of 0.2 mg/kg (up to at least 0.5 mg/kg/day) or the introduction of non-steroidal IMT (i.e., azathioprine, cyclosporine, or mycophenolate mofetil). Any intolerance to corticosteroid also determined a switch in treatment to non-steroidal IMT. Based on the predefined protocol, the term “flare” was used to describe the appearance or worsening of inflammatory signs observed at least sixth months after disease onset. During the 24-month follow-up period, the presence of ocular complications (i.e., cataract [6], ocular hypertension/glaucoma [7,8], choroidal neovascularization (CNV) [9], or SGF) was recorded. Cataract was defined as any lens opacification greater than nuclear or cortical 2+/4 or subcapsular 1+/4 [6]. Ocular hypertension was defined as an intraocular pressure (IOP) above 21mmHg [7,8]. The CNV membrane was diagnosed when increasingly localized hyperfluorescence at the posterior pole is detected on FA or a hyperreflective subretinal lesion associated with sub or intraretinal fluid on OCT.

The main outcomes measures included clinical and subclinical flares, presence of sunset glow fundus, and ff-ERG results from 12 to 24 months of follow-up.

STATISTICAL ANALYSIS PLAN WITH RESULTS INFORMATION

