For the comparison of qualitative and quantitative data between the stable ERG and worsening ERG groups, the Fisher exact test and Mann Whitney test, respectively, was used (**Tables 2 and 3**). Furthermore, Kappa statistics was used to test interrater reliability between subnormal ERG and SGF. P values ≤ 0.05 were considered statistically significant. Generalized estimated equations (GEE) were used for analyzing binary ocular data. (**Tables 2 and 3**) Data analysis and statistical tests were conducted using SPSS 20.0 (SPSS Science, Chicago, IL, USA).

Table 2 Electrotoretinogram results at 12 and 24 months (median value) and variation between 24 and 12 months in patients with Vogt-Koyanagi-Harada disease and controls

Parameters ^a	Controls (n = 61 eyes)	Patients (n = 24 eyes)				ERG-based groups						p ^d	
					p ^c	Stable (n = 17 eyes)			Worsening (n = 7 eyes)				
		T12	T24	T24-T12 ^b		T12	T24	T24-T12 ^b	T12	T24	T24-T12 ^b		
Scotopic													
^b Amplitude (μV)	211 (114–366)	201 (104–352)	189 (130–380)	8 %	0.504	192 (104–352)	210 (130–380)	9.5 %	231 (112–300)	161 (134–183)	–32.9 %	0.006	
^b Latency (ms)	77 (70–86)	89 (78–100)	89 (75–99)	–0.4 %	<0.001	90 (78–100)	89 (75–99)	–0.6 %	87 (81–92)	148 (120–262)	2.3 %	0.319	
Maximum scotopic													
^a Amplitude (μV)	300 (211–440)	210 (134–336)	189 (120–317)	–1.5 %	<0.001	203 (134–336)	224 (166–317)	7 %	215 (157–330)	148 (120–262)	–21.4 %	<0.001	
^a Latency (ms)	22 (18–23)	23 (19–25)	23 (20–55)	–0.6 %	0.008	23 (22–25)	23 (22–55)	–1.3 %	23 (19–24)	24 (20–54)	5.2 %	0.295	
^b Amplitude (μV)	510 (348–789)	508 (328–728)	484 (336–769)	–1.4 %	0.164	507 (328–728)	528 (355–769)	2.8 %	546 (398–597)	404 (336–540)	–10.8 %	0.001	
^b Latency (ms)	44 (36–50)	50 (44–62)	50 (41–55)	–2.3 %	<0.001	50 (44–62)	50 (46–55)	–1.3 %	49 (45–50)	46 (41–54)	–3.3 %	<0.001	
Oscillatory potential (μV)	121 (92–228)	92 (48–272)	114 (35–259)	0.7 %	0.215	95 (48–272)	135 (46–259)	5.9 %	88 (71–119)	55 (35–130)	–47.1 %	0.168	
Photopic													
^a Amplitude (μV)	50 (34–89)	42 (23–63)	43 (23–66)	–1 %	0.004	42 (23–60)	44 (23–66)	0 %	33 (25–63)	33 (24–52)	–5 %	0.328	
^a Latency (ms)	15 (14–17)	16 (14–17)	16 (14–17)	–2.2 %	0.005	16 (15–17)	16 (14–17)	–2.5 %	16 (14–17)	16 (14–17)	3.7 %	0.723	
^b Amplitude (μV)	227 (106–367)	202 (87–312)	186 (111–345)	–1.4 %	0.025	190 (113–312)	209 (147–345)	2.4 %	218 (87–236)	176 (111–190)	–13.6 %	0.139	

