^b Latency (ms)	31 (27–34)	31 (29–35)	31 (29–33)	–2.6 %	0.263	31 (29–35)	30 (29–33)	–1.8 %	32 (31–33)	31 (29–32)	–2.8 %	0.628	
Flicker 30 Hz	68 (42–122)	52 (24–89)	54 (29–85)	0.3 %	<0.001	53 (32–89)	55 (37–85)	6.2 %	52 (24–81)	36 (29–67)	–6.9 %	0.189	

^a ERG measures represented as median; ERG: electrotoretinography, Mann-Whitney test between ERG-based groups; ^b difference, in percentage, between values observed at 24 and 12 months was calculated for each patient and the median value is here represented; ^c p value comparing controls × patients at 24 months—generalized estimated equation with normal distribution and logarithmic link function, supposing an interchangeable correlation matrix between the eyes; ^d p value comparing T24–12 months between stable and worsening ff-ERG groups—generalized estimated equation with normal distribution and logarithmic link function, supposing an interchangeable correlation matrix between the eyes

Table 3 Electroretinogram-based groups of patients with Vogt-Koyanagi-Harada disease and their clinical characteristics

	ERG-stable group	ERG-worsening group	p
N (eyes)	17	7	
Age, years, median (range)	32 (15–42)	22 (21–67)	0.864 ^a
Interval to treatment start, days, median (range)	21 (3–51)	17 (7–33)	0.727 ^a
Visual acuity at M1(logMAR), median (range)	0.3 (0–2)	0.1 (0–0.7)	0.433 ^b
Choroidal thickness at M1, μm , median (range)	545 (308–904)	635 (303–911)	0.001 ^c
Inflammatory signs, eyes (%)			
Anterior chamber cells fluctuation	8 (47.1)	0 (0)	0.054 ^d
Choroidal thickness fluctuation, eyes (%)	8 (47.1)	4 (57.1)	0.022 ^e
Dark dots fluctuation ^o			
None	0 (0)	2 (28.6)	0.478 ^f
One	12 (70.6)	2 (28.6)	
Two	2 (11.8)	3 (42.8)	
Three	3 (17.6)	0 (0)	
Perivasculär leakage	9 (52.9)	4 (57.1)	0.936 ^e
Ocular complications, eyes (%)			
Cataract	5 (29.4)	0 (0)	0.272 ^d
Ocular hypertension	7 (41.2)	5 (71.4)	0.983 ^e
Sunset glow fundus	8 (47.1)	2 (28.6)	0.988 ^e
Neovascularization	2 (11.8)	1 (14.3)	0.853 ^e
Fibrosis	4 (23.5)	2 (28.6)	0.846 ^e
Treatment, patients (%)			
Additional NS immunosuppression	5 (55.6)	1 (33.3)	>0.999 ^d
Prednisone increment**	6 (66.7)	2 (66.7)	>0.999 ^d

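### Table 2 tests the month 12 to 24 change in scotopic amplitudes between groups that were formed from that same change, so four p-values are circular

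*Combined protocol and SAP*

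**What the plan says.** The ff-ERG methods in the Study Protocol define worsening as a reduction of more than 30% "in any scotopic ERG parameter, which needed to be confirmed in two consecutive examinations". The months 12 and 24 recordings are compared, and "all included eyes were grouped based on the worsening or stabilization of the scotopic parameters from 12th to 24th month". Table 2 has 17 stable and 7 worsening eyes.

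Table 2, footnote d, describes the last column as "p value comparing T24–12 months between stable and worsening ff-ERG groups—generalized estimated equation with normal distribution and logarithmic link function". For the scotopic amplitudes that column reads 0.006 (scotopic b), <0.001 (maximum a), 0.001 (maximum b) and 0.168 (oscillatory potential).

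The statistical section says that, for comparisons "between the stable ERG and worsening ERG groups, the Fisher exact test and Mann Whitney test, respectively, was used", and that "P values ≤ 0.05 were considered statistically significant". The main outcome measures include "ff-ERG results from 12 to 24 months of follow-up".

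**The concern.** The same eyes, the same parameters and the same interval define the groups and supply the tested variable. An eye stands in the worsening column because at least one scotopic value fell by more than 30% between months 12 and 24. Asking afterwards whether that change differs between the columns is not a fair test of equal change, whether it is done by GEE or by Mann-Whitney.

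Three of the four p-values fall below the plan's 0.05 threshold, in a domain listed as a main outcome. No available text marks them as descriptive. A reader would take them as independent evidence that scotopic function diverged between two kinds of eye.

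**Working it through.** **Reproducing the printed p-values.** This is not possible. Table 2 gives medians and ranges only, without values per eye or the pairing of eyes within patients.

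**Which rows can have defined the groups.** The largest possible fall in a row is (T12 maximum − T24 minimum) / T12 maximum. From the Table 2 ranges:

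| Latency row | Worsening eyes | Stable eyes |
|---|---|---|
| Scotopic b | (92−75)/92 = 18.5% | (100−75)/100 = 25% |
| Maximum a | (24−20)/24 = 16.7% | (25−22)/25 = 12% |
| Maximum b | (50−41)/50 = 18% | (62−46)/62 = 25.8% |

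None reaches 30%, so only the four scotopic amplitude rows can have defined the groups. The Study Protocol lists oscillatory potentials among the scotopic responses.

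The scotopic b latency bound for worsening eyes uses the all-patient T24 minimum of 75, because the worsening T24 cell, 148 (120–262), is a misprint. It repeats the maximum a amplitude cell and lies wholly outside the all-patient T24 range of 75–99. It would also imply 148/87 − 1 = +70%, where the printed median change is 2.3%.

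**What the grouping alone implies for scotopic b amplitude.** Read the medians as medians over eyes.

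- The worsening median of −32.9% is the fourth of seven values, so at least 4 eyes fell by more than 30%.
- The worsening T12 minimum is 112 and the T24 minimum is 134. The eye at 112 must therefore have risen by at least 134/112 − 1 = 19.6%. That exceeds the stable median of 9.5%, so it exceeds at least 9 of the 17 stable eyes.
- Assume that no stable eye fell by more than 30%. Four worsening eyes then rank below all stable eyes. The other three can be placed among 17 stable eyes in C(20,3) = 1,140 ways. Removing the C(11,3) = 165 in which none ranks above 9 stable eyes leaves 975.
- For 7 v 17 eyes the exact two-sided Mann-Whitney p is 0.047 at U = 28 and 0.055 at U = 29. In 539 of the 975 placements (55%) p ≤ 0.05. The median U is 27 (p = 0.040).
- With five eyes fixed lowest, C(19,2) − C(10,2) = 171 − 45 = 126 placements remain, and 114 (90%) give p ≤ 0.05.

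These shares weight placements equally and are not probabilities. The oscillatory potential row gives the same 975 placements: its median is −47.1%, and its forced riser, 130/119 − 1 = +9.2%, exceeds the stable median of 5.9%. Its printed p is nevertheless 0.168.

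**Simulation with no true change.** Taken from the documents: 12 patients (inferred from the Table 3 treatment denominators, 9 + 3), two eyes each, four scotopic amplitudes and the 30% rule. Assumed: a visit log-SD of 0.15 to 0.25, the correlations below, at least 3 eyes per group, and confirmation of the same parameter at months 18 and 24. The confirming visits are not named. Months 18 and 24 follow from ERGs being done "at 30 days and at 6 months intervals thereafter". The GEE is read as a log-link normal model on raw amplitudes with a group-by-visit term.

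| Correlation between parameters / between eyes | Mann-Whitney p ≤ 0.05 | GEE p ≤ 0.05 |
|---|---|---|
| 0 / 0 | 14–15% | 28–30% |
| 0.2 / 0.5 | 27–30% | 45–46% |
| 0.5 / 0.5 | 52–54% | 69–76% |
| 0.8 / 0.5 | 80–88% | 95–98% |
| Random labels | 3–5% | 13–20% |

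The rates are per amplitude. The random-label GEE rate shows that part of the GEE excess over 5% is small-sample error with about 12 patients.

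A second simulation used different assumptions: SD of percent change 33 to 50, inter-parameter correlation 0 to 0.8, inter-eye correlation 0.5, a confirming examination, and 5 to 9 worsening eyes. Mann-Whitney gave p ≤ 0.05 in 20–89% of runs per amplitude, against about 4–7% for a variable unrelated to the grouping.

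**The case against.** **The circularity is partial in each row.** Any one parameter is enough to classify an eye. The worsening medians are −21.4% for maximum a and −10.8% for maximum b, so in each of those rows at least 4 of 7 eyes did not fall by more than 30%. Those rows may carry some information on whether loss extends across parameters. The confirmation rule weakens the effect further. This stands, but partial selection on the outcome still leaves a p-value without its nominal meaning.

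**The size is not established by the documents.** The simulation inputs are assumed. The placement count uses Mann-Whitney where footnote d specifies a GEE, and a stable eye could have had an unconfirmed 30% fall. Footnote b describes the change as a "difference, in percentage, between values observed at 24 and 12 months was calculated for each patient and the median value is here represented". If the medians are over patients, the count of eyes fails. All of this stands, and the calculations are illustrations only. The structural point does not depend on them.

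**Noise may be a poor account of these data.** Confirmed noise alone gave 7 or more worsening eyes in only 0–28% of runs. This also stands: real deterioration is not excluded.

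**The harm is limited.** One of the four p-values is not significant. The main outcome could be read as the classification itself, and no available text draws a conclusion from these tests. One part of the statistical section was not available and may hold a caveat. This limits how serious the point is. The p-values are still printed in Table 2 beside a 0.05 rule.

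**Conclusion.** The concern holds. The footnote-d p-values for scotopic b, maximum a, maximum b and oscillatory potential amplitude test a difference that the grouping rule partly creates, and they should not be read at 0.05. This conclusion rests on the definitions alone and is secure.

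The size is uncertain. Under the assumed inputs every simulated setting exceeded its random-label rate, from 14% at the lowest to 88% at the highest by Mann-Whitney. A firmer figure would need per-eye data.

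The finding does not show that the worsening eyes were stable. Footnote c (controls v patients) is unaffected, and the Table 3 comparisons are not circular in this way. The oscillatory potential result shows that circularity does not guarantee significance. The point should be fixed, but it is confined to these four p-values.

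**What to change.** Remove the footnote-d p-values from the four scotopic amplitude rows, keep the medians and ranges, and label those rows as describing how the groups were formed. Keep the between-group tests for variables that did not form the groups. Mark the photopic and flicker tests (p from 0.139 to 0.723) as exploratory, since those parameters may correlate with scotopic change.

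Three separate checks in the same table are worth making at the same time:

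- Correct the scotopic b latency cell for worsening eyes at month 24.
- Verify the p < 0.001 for maximum b latency, where the median changes are only −1.3% and −3.3%.
- State in footnote d whether the GEE response is the raw value or the T24−T12 difference. A log link cannot give a negative mean difference, and several worsening-group median changes are negative.

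The cost is a table and footnote edit, one corrected cell and one p-value checked against existing data. No new analysis is needed. The price is that the four rows lose their between-group p-values.

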For the comparison of qualitative and quantitative data between the stable ERG and worsening ERG groups, the Fisher exact test and Mann Whitney test, respectively, was used (**Tables 2 and 3**). Furthermore, Kappa statistics was used to test interrater reliability between subnormal ERG and SGF. P values ≤ 0.05 were considered statistically significant. Generalized estimated equations (GEE) were used for analyzing binary ocular data. (**Tables 2 and 3**) Data analysis and statistical tests were conducted using SPSS 20.0 (SPSS Science, Chicago, IL, USA).

Table 2 Electrotoretinogram results at 12 and 24 months (median value) and variation between 24 and 12 months in patients with Vogt-Koyanagi-Harada disease and controls

Parameters ^a	Controls (n = 61 eyes)	Patients (n = 24 eyes)				ERG-based groups						p ^d	
					p ^c	Stable (n = 17 eyes)			Worsening (n = 7 eyes)				
		T12	T24	T24-T12 ^b		T12	T24	T24-T12 ^b	T12	T24	T24-T12 ^b		
Scotopic													
^b Amplitude (μV)	211 (114–366)	201 (104–352)	189 (130–380)	8 %	0.504	192 (104–352)	210 (130–380)	9.5 %	231 (112–300)	161 (134–183)	–32.9 %	0.006	
^b Latency (ms)	77 (70–86)	89 (78–100)	89 (75–99)	–0.4 %	<0.001	90 (78–100)	89 (75–99)	–0.6 %	87 (81–92)	148 (120–262)	2.3 %	0.319	
Maximum scotopic													
^a Amplitude (μV)	300 (211–440)	210 (134–336)	189 (120–317)	–1.5 %	<0.001	203 (134–336)	224 (166–317)	7 %	215 (157–330)	148 (120–262)	–21.4 %	<0.001	
^a Latency (ms)	22 (18–23)	23 (19–25)	23 (20–55)	–0.6 %	0.008	23 (22–25)	23 (22–55)	–1.3 %	23 (19–24)	24 (20–54)	5.2 %	0.295	
^b Amplitude (μV)	510 (348–789)	508 (328–728)	484 (336–769)	–1.4 %	0.164	507 (328–728)	528 (355–769)	2.8 %	546 (398–597)	404 (336–540)	–10.8 %	0.001	
^b Latency (ms)	44 (36–50)	50 (44–62)	50 (41–55)	–2.3 %	<0.001	50 (44–62)	50 (46–55)	–1.3 %	49 (45–50)	46 (41–54)	–3.3 %	<0.001	
Oscillatory potential (μV)	121 (92–228)	92 (48–272)	114 (35–259)	0.7 %	0.215	95 (48–272)	135 (46–259)	5.9 %	88 (71–119)	55 (35–130)	–47.1 %	0.168	
Photopic													
^a Amplitude (μV)	50 (34–89)	42 (23–63)	43 (23–66)	–1 %	0.004	42 (23–60)	44 (23–66)	0 %	33 (25–63)	33 (24–52)	–5 %	0.328	
^a Latency (ms)	15 (14–17)	16 (14–17)	16 (14–17)	–2.2 %	0.005	16 (15–17)	16 (14–17)	–2.5 %	16 (14–17)	16 (14–17)	3.7 %	0.723	
^b Amplitude (μV)	227 (106–367)	202 (87–312)	186 (111–345)	–1.4 %	0.025	190 (113–312)	209 (147–345)	2.4 %	218 (87–236)	176 (111–190)	–13.6 %	0.139	
^b Latency (ms)	31 (27–34)	31 (29–35)	31 (29–33)	–2.6 %	0.263	31 (29–35)	30 (29–33)	–1.8 %	32 (31–33)	31 (29–32)	–2.8 %	0.628	
Flicker 30 Hz	68 (42–122)	52 (24–89)	54 (29–85)	0.3 %	<0.001	53 (32–89)	55 (37–85)	6.2 %	52 (24–81)	36 (29–67)	–6.9 %	0.189	

^a ERG measures represented as median; ERG: electrotoretinography, Mann-Whitney test between ERG-based groups; ^b difference, in percentage, between values observed at 24 and 12 months was calculated for each patient and the median value is here represented; ^c p value comparing controls × patients at 24 months—generalized estimated equation with normal distribution and logarithmic link function, supposing an interchangeable correlation matrix between the eyes; ^d p value comparing T24–12 months between stable and worsening ff-ERG groups—generalized estimated equation with normal distribution and logarithmic link function, supposing an interchangeable correlation matrix between the eyes

Table 3 Electroretinogram-based groups of patients with Vogt-Koyanagi-Harada disease and their clinical characteristics

	ERG-stable group	ERG-worsening group	p
N (eyes)	17	7	
Age, years, median (range)	32 (15–42)	22 (21–67)	0.864 ^a
Interval to treatment start, days, median (range)	21 (3–51)	17 (7–33)	0.727 ^a
Visual acuity at M1(logMAR), median (range)	0.3 (0–2)	0.1 (0–0.7)	0.433 ^b
Choroidal thickness at M1, μm , median (range)	545 (308–904)	635 (303–911)	0.001 ^c
Inflammatory signs, eyes (%)			
Anterior chamber cells fluctuation	8 (47.1)	0 (0)	0.054 ^d
Choroidal thickness fluctuation, eyes (%)	8 (47.1)	4 (57.1)	0.022 ^e
Dark dots fluctuation ^o			
None	0 (0)	2 (28.6)	0.478 ^f
One	12 (70.6)	2 (28.6)	
Two	2 (11.8)	3 (42.8)	
Three	3 (17.6)	0 (0)	
Perivasculär leakage	9 (52.9)	4 (57.1)	0.936 ^e
Ocular complications, eyes (%)			
Cataract	5 (29.4)	0 (0)	0.272 ^d
Ocular hypertension	7 (41.2)	5 (71.4)	0.983 ^e
Sunset glow fundus	8 (47.1)	2 (28.6)	0.988 ^e
Neovascularization	2 (11.8)	1 (14.3)	0.853 ^e
Fibrosis	4 (23.5)	2 (28.6)	0.846 ^e
Treatment, patients (%)			
Additional NS immunosuppression	5 (55.6)	1 (33.3)	>0.999 ^d
Prednisone increment**	6 (66.7)	2 (66.7)	>0.999 ^d

^aMann-Whitney; ^bgeneralized estimated equation with normal distribution and logarithmic link function, supposing an interchangeable correlation matrix between the eyes; ^cgeneralized estimated equation with normal distribution and identity link function, supposing an interchangeable correlation matrix between the eyes; ^dFisher exact test; ^egeneralized estimated equation with binomial distribution and logit link function, supposing an interchangeable correlation matrix between the eyes; ^fgeneralized estimated equation with Poisson distribution and identity link function supposing an interchangeable correlation matrix between the eyes; ^oincrease in the number of DD by region, whether in the posterior pole or in each quadrant, followed by a diminishment. Objectively was defined as a variation in the final score between two different points in time ≥ 0.5 (Tugal-Tutkun et al., 2010). NS, non-steroidal; **two patients that received increment in prednisone dose presented one eye in stable and one eye in worsening groups

REFERENCES

- [1] R. W. Read et al., “Revised Diagnostic Criteria for Vogt-Koyanagi-Harada Disease: Report of an International Committee on Nomenclature,” *Am. J. Ophthalmol.*, vol. 131, pp. 647–652, 2001.
- [2] F. T. da Silva, C. E. Hirata, E. Olivalves, M. K. Oyamada, and J. H. Yamamoto, “Fundus-based and electroretinographic strategies for stratification of late-stage Vogt-Koyanagi-Harada disease patients. *Am J Ophthalmol* 148(6):939–945
- [3] I. Tugal-Tutkun, C. P. Herbort, and M. Khairallah, “Scoring of dual fluorescein and ICG inflammatory angiographic signs for the grading of posterior segment inflammation (dual fluorescein and ICG angiographic scoring system for uveitis),” *Int. Ophthalmol.*, vol. 30, no. 5, pp. 539–52, Oct. 2010.
- [4] D. L. McCulloch et al., “ISCEV Standard for full-field clinical electroretinography (2015 update),” *Doc. Ophthalmol.*, vol. 130, pp. 1–12, 2015.
- [5] E. L. Berson et al., “Natural Course of Retinitis Pigmentosa Over a Three Year Interval,” *Am. J. Ophthalmol.*, vol. 99, no. 3, pp. 240–251, 1985.
- [6] L. T. Chylack, J. K. Wolfe, D. M. Singer, M. C. Leske, M. a Bullimore, and L. Ian, “Opacities Classification,” *Arch. Ophthalmol.*, vol. 111, pp. 831– 836, 1993.

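### Table 2 footnotes b and d together describe a log-link normal GEE for a signed change that must average below zero in one row printed as significant, while other text names Mann-Whitney; the model or its description needs correcting

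*Combined protocol and SAP*

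**What the plan says.** Three places describe the comparison of the stable (17 eyes) and worsening (7 eyes) groups in Table 2.

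- **Footnote d**, attached to the last p column: "p value comparing T24–12 months between stable and worsening ff-ERG groups—generalized estimated equation with normal distribution and logarithmic link function", with an exchangeable correlation between eyes.
- **Footnote a**, attached to the parameter header: "Mann-Whitney test between ERG-based groups".
- **The statistical paragraph above Table 2**, which cites Tables 2 and 3: "For the comparison of qualitative and quantitative data between the stable ERG and worsening ERG groups, the Fisher exact test and Mann Whitney test". It then adds: "Generalized estimated equations (GEE) were used for analyzing binary ocular data".

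Footnote b defines the T24-T12 column: "difference, in percentage, between values observed at 24 and 12 months was calculated for each patient and the median value is here represented". Many of its entries are negative.

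Footnote c uses the same distribution and link for a different comparison: "p value comparing controls × patients at 24 months—generalized estimated equation with normal distribution and logarithmic link function". That response is a level and is always positive.

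Table 3 footnote c, used for choroidal thickness, has a GEE with "normal distribution and identity link function, supposing an interchangeable correlation matrix between the eyes".

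**The concern.** A log link sets the fitted mean to exp(linear predictor), which is always above zero. A percentage or μV change can average below zero, and in a group selected for deterioration it is likely to. Applied as written, footnotes b and d describe a model that cannot reproduce a negative group mean. In such a case the group coefficient tends to drift towards minus infinity, or the fit fails.

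The ff-ERG result from 12 to 24 months is one of the named main outcomes, and this column holds all 12 of its between-group p-values. Mann-Whitney, the other test named, treats the 24 eyes as independent, although Table 3 reports that "two patients that received increment in prednisone dose presented one eye in stable and one eye in worsening groups". A reader of the available text cannot tell which analysis produced the column.

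**Working it through.** The printed p-values cannot be reproduced without eye-level data. What can be checked is whether the printed summaries force a negative group mean. A negative median alone does not.

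**Inputs** (Table 2, worsening group, n=7, median (range) in μV):

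| Row | T12 | T24 | Median change | Printed p |
|---|---|---|---|---|
| Scotopic b amplitude | 231 (112–300) | 161 (134–183) | -32.9% | 0.006 |
| Maximum scotopic a amplitude | 215 (157–330) | 148 (120–262) | -21.4% | <0.001 |
| Maximum scotopic b amplitude | 546 (398–597) | 404 (336–540) | -10.8% | 0.001 |

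*Input check.* The T24 cell 148 (120–262) is printed in two rows. Its minimum matches the all-patient T24 range for maximum scotopic a amplitude (120–317), so it is relied on only there. In the scotopic b latency row it lies outside the all-patient T24 range (75–99), so that cell supports no conclusion. The T24 minimum of 336 for maximum scotopic b amplitude matches the all-patient range 336–769.

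**Bound on the mean change in μV.** With 7 ordered values and known minimum, median and maximum:

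- highest possible mean = (min + 3×median + 3×max)/7
- lowest possible mean = (3×min + 3×median + max)/7

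The highest possible mean change is the highest T24 mean minus the lowest T12 mean. Rounding of ±0.5 at each visit adds at most 1.0.

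- Maximum scotopic b amplitude: (336 + 3×404 + 3×540)/7 − (3×398 + 3×546 + 597)/7 = 452.57 − 489.86 = −37.29; with rounding **−36.3 μV**.
- Scotopic b amplitude: (134 + 3×161 + 3×183)/7 − (3×112 + 3×231 + 300)/7 = 166.57 − 189.86 = −23.29; with rounding −22.3 μV.
- Maximum scotopic a amplitude: (120 + 3×148 + 3×262)/7 − (3×157 + 3×215 + 330)/7 = 192.86 − 206.57 = −13.71; with rounding −12.7 μV.

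**Bound on the mean percentage change.** The mean ratio is greatest when the largest T24 values are paired with the smallest T12 values.

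- Maximum scotopic b amplitude: (3×540/398 + 3×404/546 + 336/597)/7 − 1 = −2.1%. With rounding: (3×540.5/397.5 + 3×404.5/545.5 + 336.5/596.5)/7 − 1 = **−1.9%**.
- Scotopic b amplitude: +6.3% as printed, +7.0% with rounding. Not forced negative.
- Maximum scotopic a amplitude: +6.2% as printed, +6.8% with rounding. Not forced negative.

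**All rows, both groups.** After rounding, these three worsening-group cells are the only ones of 24 forced negative in absolute units. Maximum scotopic b amplitude is the only one forced negative in percent. Oscillatory potential (−0.86 as printed, +0.14 with rounding) and photopic b latency (−0.57, +0.43) drop out. No stable-group cell is forced negative.

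**Patients with one eye in each group.** Table 3 counts treatment in patients: 5 (55.6%) implies 5/0.556 = 9, and 1 (33.3%) implies 1/0.333 = 3, so 12 in all. If each contributes two eyes, there are 24 eyes. A patient with both eyes in the same group adds two eyes to that group, so with 17 and 7 eyes the number of split patients must be odd. Table 3 reports two among those with a prednisone increment, which makes it 3, 5 or 7.

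**The case against.** The strongest reply is that footnote d does not name the response variable. Footnote b defines the displayed column, not necessarily the GEE outcome. A log-link model of the positive T12 and T24 levels with a group-by-time term would compare the change between groups validly, and footnote c's identical wording for levels supports that reading. A log-link model of the ratio T24/T12 would also be valid. This stands, and it makes the defect conditional. It does not clear footnote d, which mentions neither levels, nor an interaction, nor a ratio, and gives a correlation between eyes but not between visits. Part of the analysis section was not available for this review, so the lack of a fuller specification is not itself counted as an error.

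Second, the bounds apply to the unweighted mean over eyes, whereas an exchangeable GEE can weight eyes differently. This also stands. In a search over invented eye-level data roughly matching the row, one log-link fit converged with a worsening mean of about +9% while the unweighted mean was about −7%. Such cases were rare (roughly 0.1–0.3% of draws in a search set up to favour them), so they show possibility only. Equally, one illustrative data set on which the log-link GEE failed and the identity-link GEE converged used invented stable values and pairing, and does not show what happened in the trial.

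Third, the test conflict may be an editing remnant. The GEE sentence cites Table 2, which holds only continuous measures, so the reference to binary data may have meant two-eye data. That is plausible, but the Mann-Whitney wording remains and contradicts footnote d.

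Finally, the count of split patients is less firm than the two reported directly. Table 3's denominators of 9 and 3 fit no uniform rule for placing such patients: if all were counted in the worsening group, 3 patients could not supply 7 eyes; if all were counted in the stable group, only one patient would be split.

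**Conclusion.** The concern holds in conditional form. Footnotes b and d, read together, describe a model that cannot represent the worsening group's unweighted mean change in maximum scotopic b amplitude, which is at most −36.3 μV or −1.9%. Either the model was unsuitable (signed change modelled) or footnote d misdescribes a valid one (levels or ratio modelled). The separate naming of Mann-Whitney for the same comparison is an inconsistency under every reading.

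The bounds assume that all 7 eyes contribute at both visits and that printed values are rounded to the nearest μV.

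A reader might infer that p=0.001, or the whole column, is wrong. The documents do not support that: the modelled response is not stated, valid log-link models exist, and GEE weighting means that even a fit to the changes need not fail. A reader might also extend the problem to every row with a negative median; on footnote b's percentage scale only one row is forced negative. This should be fixed because it concerns a main outcome.

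**What to change.** State the response, scale and model terms behind footnote d, then follow the case that applies.

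- **Signed change modelled:** re-run all 12 rows with a normal, identity-link GEE clustered on patient, as in Table 3 footnote c, and replace the p-values.
- **Levels modelled with a group-by-time term:** keep the p-values provided the model accounts for the two visits per eye as well as the two eyes per patient, and reword footnote d to say so.
- **Ratio T24/T12 modelled:** keep the p-values and reword footnote d.

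In every case, remove the Mann-Whitney wording for eye-level comparisons in Table 2 from footnote a and the statistical paragraph, and name the patient-clustered method. At least two patients have one eye in each group, and three or more if the 12 patients implied by Table 3 each contribute two eyes.

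The cost is a few lines of wording or a short re-run. After a re-run some p-values may change; which ones cannot be told from the printed figures. The fix does not remove a separate circularity: the groups were defined by scotopic change from 12 to 24 months, and all four rows with p≤0.05 in this column (0.006, <0.001, 0.001, <0.001) are scotopic.
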